APPENDIX 8. TYPE 2 DIABETES MEDICAL HISTORY AND PRIOR MEDICATION

MedDRA Preferred Terms for Type 2 Diabetes	
	Acquired lipoatrophic diabetes
	Diabetes complicating pregnancy
	Diabetes mellitus
	Diabetes mellitus inadequate control
	Diabetes mellitus malnutrition-related
	Diabetes with hyperosmolarity
	Diabetic arteritis
	Diabetic coma
	Diabetic complication
	Diabetic dyslipidaemia
	Diabetic endorgan damage
	Diabetic coronary microangiopathy
	Diabetic hepatopathy
	Diabetic hyperglycaemic coma
	Diabetic hyperosmolar coma
	Diabetic ketoacidosis
	Diabetic ketoacidotic hyperglycaemic coma
	Diabetic ketosis
	Diabetic wound
	Diabetic metabolic decompensation
	Euglycaemic diabetic ketoacidosis
	Fulminant type 1 diabetes mellitus
	Insulin resistant diabetes
	Insulin-requiring type 2 diabetes mellitus
	Ketosis-prone diabetes mellitus
	Latent autoimmune diabetes in adults
	Monogenic diabetes
	New onset diabetes after transplantation
	Pancreatogenous diabetes
	Steroid diabetes
	Type 1 diabetes mellitus
	Type 2 diabetes mellitus
	Type 3 diabetes mellitus

Medication (WHODrug ATC4) for Type 2 Diabetes	
A10AB	Insulins and Analogues for Injection, Fast-Acting
A10AC	Insulins and Analogues for Injection, Intermediate-Acting
A10AD	Insulins and Analogues for Injection, Intermediate- or Long-Acting Combined with Fast-Acting
A10AE	Insulins and Analogues for Injection, Long-Acting
A10AF	Insulins and Analogues for Inhalation
A10BA	Biguanides
A10BB	Sulfonylureas
A10BC	Sulfonamides (Heterocyclic)
A10BD	Combinations of Oral Blood Glucose Lowering Drugs
A10BF	Alpha-Glucosidase Inhibitors
A10BG	Thiazolidinediones
A10BH	Dipeptidyl Peptidase-4 (DPP-4) Inhibitors
A10BJ	Glucagon-Like Peptide-1 (GLP-1) Analogues
A10BK	Sodium-Glucose Co-Transporter 2 (SGLT2) Inhibitors
A10BX	Other Blood Glucose Lowering Drugs, Excl. Insulins

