 - Carotid endarterectomy, carotid stenting, or more than 70% stenosis in a carotid artery determined by carotid ultrasound or angiogram (Note: If stenosis assessed by carotid ultrasound is reported as range between 60%-79%, patient may qualify only if internal carotid artery peak systolic velocity is >230 cm/sec), occurring greater than 90 days prior to screening, **or**
- b. High risk for a CVD event (ie, high-risk primary prevention)
 - Reynolds Risk score >30% or a SCORE Risk score >7.5% over 10 years (see Appendix 3 and Appendix 4 for additional details), **or**
 - Coronary artery calcium score >400 Agatston units (AU) at any time in the past, **or**
 - Patients with type 1 or type 2 diabetes, aged >65 years (women) or >60 years (men).

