15.4. Analysis Populations

The Full Analysis Set (FAS), used for all of the efficacy analyses and summaries, is defined as all randomized patients and is also known as the intention-to-treat (ITT) set of patients. Patients in the FAS will be included in their randomized treatment group, regardless of the treatment they actually received.

The Safety Population (SP), used for all of the safety summaries, is defined as all randomized patients who received at least 1 dose of study medication (investigational product). Patients in the SP will be included in the treatment group that they actually received, regardless of their randomized treatment.

The Diabetes Efficacy Population, used for efficacy analyses of HbA_{1C} and fasting glucose, is defined as the subset of patients in the FAS fulfilling one or more of the following criteria at baseline captured by information recorded as medical history, prior medication, and/or laboratory data:

- Medical history indicating type 2 diabetes
- Prior glucose-lowering medication with confirmation of diagnosis of diabetes by a DC (Section 14.4) if prior medication is the only criteria met for diagnosis of diabetes
- HbA_{1C} measurement $\geq 6.5\%$
- Two or more measurements of fasting glucose ≥ 126 mg/dL (7.0 mmol/L)

The Inadequately Controlled Diabetes Efficacy Population, is defined as the subset of patients in the Diabetes Efficacy Population with an HbA_{1C} of 7% or greater at baseline. This efficacy population will be used for the corresponding diabetes secondary and tertiary endpoints.

The Prediabetes Efficacy Population, used for efficacy analyses of time to new-onset diabetes and for efficacy analyses of HbA_{1C} and fasting glucose, is defined as the subset of patients in the FAS fulfilling all of the following criteria at baseline captured by information recorded as medical history, prior medication, and/or laboratory data:

- Having no medical history indicating type 2 diabetes
- Having no prior glucose-lowering medication unless verified by the DC that there is no diagnosis of diabetes (Section 14.4) if prior medication is the only criteria assessed for the diagnosis of diabetes
- HbA_{1C} measurement of 5.7% to 6.4% or 1 or more measurements of fasting glucose of 100 mg/dL (5.6 mmol/L) to 125 mg/dL (6.9 mmol/L), but not more than 1 value of fasting glucose ≥ 126 mg/dL (7.0 mmol/L).

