3.2.3. Secondary Efficacy Lipid and Biomarker Endpoints

- Percent change from baseline to Month 6 in LDL-C
- Percent change from baseline to Month 6 in hs-CRP
- Change from baseline to Month 12 in HbA_{1C} in patients with inadequately controlled type 2 diabetes mellitus

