7.4. Diabetes Related Definitions

7.4.1. Baseline Glycemic Status

Analyses of diabetes and related biomarkers are conducted with specific subsets of study population based on the baseline glycemic status defined in Table 1.

- For efficacy analyses of new-onset type 2 diabetes (conducted in the study population with No Diabetes at baseline), and related biomarkers HbA1c and fasting glucose, the FAS (or PPS for sensitivity analyses) is used with subpopulations defined according to the baseline glycemic status.
- For safety analyses of AESIs of *new-onset diabetes* (conducted in the study population with No Diabetes at baseline), and *worsening hyperglycemia* (Diabetes at baseline), and related safety laboratory measures including HbA1c and fasting glucose, the SAS is used with subpopulations defined according to the baseline glycemic status.

Table 1: Baseline Glycemic Status

Status	Definition
Diabetes	Meeting 1 or more of the following criteria at baseline captured by information recorded prior to Day 1: 
 • Medical history or adverse events indicating diabetes as defined in the Diabetes Committee Charter (attached as Appendix 8) • Prior glucose-lowering medication as defined by the Diabetes Committee Charter (attached as Appendix 8) • HbA_{1C} measurement $\geq 6.5\%$ • Two or more measurements of fasting glucose ≥ 126 mg/dL (7.0 mmol/L)
Inadequately Controlled (IC) Diabetes	With Diabetes and a HbA _{1C} of 7% or greater at baseline.
No Diabetes	Not meeting any of the criteria for Diabetes at baseline.
Prediabetes	No Diabetes at baseline, and with: 
 • HbA_{1C} measurement of $\geq 5.7\%$ and $< 6.5\%$, OR • 1 or more measurements of fasting glucose ≥ 100 mg/dL (5.6 mmol/L), but not more than 1 value of fasting glucose ≥ 126 mg/dL (7.0 mmol/L).
Normoglycemia	No Diabetes, and not meeting the criteria for Prediabetes at baseline.

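### The Month 12 HbA1c endpoint is worded for type 2 diabetes, but the set in which it is analysed has no restriction by diabetes type

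*SAP*

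**What the plan says.** **Endpoint.** SAP 3.2.3 defines the HbA1c change to Month 12 "in patients with inadequately controlled type 2 diabetes mellitus". Protocol 5.2.3 and the objectives in Protocol 5.1.2 and SAP 2.2 also name type 2. Protocol 6.2 makes HbA1c reduction in the inadequately controlled subpopulation a study hypothesis.

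**Analysed set.** SAP 15.3.4 makes the Inadequately Controlled Diabetes subgroup the one of primary interest. SAP Table 1 (section 7.4.1) defines it as Diabetes status plus baseline HbA1c of 7% or more. Any one of four criteria gives Diabetes status:
- history, worded as "Medical history or adverse events indicating diabetes as defined in the Diabetes Committee Charter (attached as Appendix 8";
- prior glucose-lowering medication, from the same appendix;
- HbA1c of at least 6.5%;
- two or more fasting glucose values of at least 126 mg/dL.

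**Term list.** The history list in SAP Appendix 8 is headed "MedDRA Preferred Terms for Type 2 Diabetes". It includes the plain type 1 term, "Fulminant type 1 diabetes mellitus" and "Latent autoimmune diabetes in adults", as well as monogenic, pancreatogenous, steroid and type 3 diabetes. The medication list includes the insulin classes.

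**Eligibility.** Inclusion criterion 7b (Protocol 7.1) admits "Patients with type 1 or type 2 diabetes, aged >65 years (women) or >60 years (men". The only glycaemic exclusion in Protocol 7.2 is HbA1c of 10% or more at screening.

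**Protocol population.** Protocol 15.4 lists "Medical history indicating type 2 diabetes" as one of four alternative criteria. HbA1c of at least 6.5% is another and carries no type restriction. Under Protocol 15.1 the SAP prevails where the two documents differ on analysis.

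**The concern.** The endpoint names one population and the analysis uses a wider one. Followed as written, the plan would report a result for inadequately controlled type 2 diabetes from a set that admits type 1 patients.

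The protocol's rationale for a glycaemic effect (section 4.2.1) rests on hepatic fatty acid synthesis, inflammation and insulin resistance. A smaller effect in type 1 diabetes is therefore plausible, although the documents do not say so. If it is smaller, including these patients pulls the estimated difference towards zero and costs precision in relation to the type 2 effect. Even if it is not, the label on the result would be inaccurate.

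**Working it through.** The plan states no figure on this point, so there is none to reproduce. The check has two parts.

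**1. Which route lets type 1 patients in?**

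Table 1 as logic: Diabetes = history OR medication OR HbA1c ≥6.5% OR two high glucose values. Inadequately Controlled = Diabetes AND HbA1c ≥7%.

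Any patient with HbA1c ≥7% also has HbA1c ≥6.5%, so the Diabetes condition is met before history or medication is looked at. The subgroup therefore reduces to everyone with baseline HbA1c ≥7%.

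To confirm, take a patient with a type 1 history over 2 medication states × 8 HbA1c values (5.5, 6.0, 6.4, 6.5, 6.9, 7.0, 8.0 and 9.9%) × 2 glucose states = 32 profiles. Classify each with the type 1 terms in Appendix 8 and again with them deleted.
- Inadequately Controlled status changes in 0 of 32 profiles.
- Diabetes status changes in 3 of 32: no medication, glucose criterion not met, and HbA1c of 5.5, 6.0 or 6.4%.

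The four criteria in Protocol 15.4 give the same result, because HbA1c ≥6.5% suffices there too.

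**2. How large is the effect?**

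Neither document gives the share p of type 1 patients in the subgroup. Assume p = 2%, 5% or 10%, no HbA1c effect in type 1, equal residual variance in both types, and p balanced between arms. Take an all-type-2 set of the same total size as the reference (information = 1).
- Estimate with type 1 included: (1 − p) × type 2 effect.
- Relative information with type 1 included: (1 − p)².
- Relative information with type 1 excluded: full effect, sample reduced to 1 − p, so 1 − p.
- Included relative to excluded: (1 − p)² / (1 − p) = 1 − p.

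| p | Effect retained | Information, included | Information, excluded | Included / excluded |
|---|---|---|---|---|
| 2% | 0.98 | 0.9604 | 0.98 | 0.98 |
| 5% | 0.95 | 0.9025 | 0.95 | 0.95 |
| 10% | 0.90 | 0.8100 | 0.90 | 0.90 |

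Keeping the type 1 patients loses 2%, 5% or 10% of the information that the analysis would have without them.

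**The case against.** **The broad list is deliberate.** The Table 1 criterion refers to diabetes, not type 2, and the list keeps people with existing diabetes of any kind out of the risk set for new-onset diabetes. This stands, and the terms should remain for that use. It does not justify reporting the HbA1c result as a type 2 result.

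**Appendix 8 as the cause.** A reader might infer that the type 1 terms under a type 2 heading are what put these patients into the HbA1c analysis. The documents do not support that: the terms are one sufficient route, but membership is the same without them. What is wrong in the appendix itself is its heading.

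**Protocol against SAP.** A reader might also infer that the protocol requires a history of type 2 diabetes and that the SAP dropped this. Protocol 15.4 needs only one of four criteria, so for this endpoint both documents have the same gap.

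**Size.** One could quote a loss of 1 − (1 − p)², about 4%, 10% or 19%. That compares against a set of the same size made up entirely of type 2 patients, which exclusion cannot provide. The recoverable part is about half. The share and the nil effect are both assumed.

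**Other analyses.** SAP 7.4.2 provides a sensitivity analysis without patients whose antidiabetic medication changed. That addresses medication changes but does not select on diabetes type. SAP 15.4.4, on additional diabetes analyses, appears in the contents, but its text is not in the version available, so a type 2-only analysis there cannot be ruled out. It would not change the main set in 15.3.4.

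**Importance.** The endpoint lies outside the seven-step hierarchy and its p-value is nominal (Protocol 15.7, SAP 8.3). This stands and limits the weight of the point.

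**Conclusion.** The mismatch is real and follows from the text alone: the endpoint is worded for type 2 diabetes, type 1 patients are eligible, and every type 1 patient with baseline HbA1c of 7% or more falls into the analysed set. The gap is the missing type restriction in SAP Table 1, shared with Protocol 15.4.

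Its numerical size cannot be taken from the documents. Under the assumptions above, attenuation and recoverable information are each about 2%, 5% or 10%. With few type 1 patients, or a similar effect in them, the estimate would hardly move and the issue would be mainly one of labelling. The primary and key secondary MACE analyses are unaffected. It is worth correcting because the correction is cheap, not because a main conclusion depends on it.

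**What to change.** 1. In SAP Table 1 and section 15.3.4, exclude from the Diabetes and Inadequately Controlled Diabetes HbA1c efficacy sets any patient with a type 1, fulminant type 1 or latent autoimmune diabetes term, whichever other criterion is met. Say that these patients do not move to the No Diabetes set.
2. State how the other non-type-2 terms (monogenic, pancreatogenous, steroid, type 3) are handled in those two sets.
3. Keep the full Appendix 8 list, retitled as covering any diabetes, to define the No Diabetes set and the new-onset diabetes risk set.
4. Align Protocol 15.4 if it is amended; otherwise the SAP governs.

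The cost is SAP wording and one flag from coded history already collected, set before unblinding, when SAP section 6 finalises the analysis sets. The HbA1c set becomes slightly smaller. Type 1 patients coded only under an unspecific term, such as plain diabetes mellitus, would remain, and the SAP should acknowledge this.

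If the sponsor prefers to keep the wider set, the consistent alternative is to reword the endpoint as diabetes of any type and add a type 2-only sensitivity analysis.

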APPENDIX 10. POTENTIALLY CLINICALLY SIGNIFICANT LABORATORY AND VITAL SIGN ABNORMALITIES

Parameter	Criteria
ALT, AST, and Total Bilirubin ^a	ALT >3× ULN AST >3× ULN TB >2× ULN
ALP	ALP >1.5× ULN
CK	>5× ULN
eGFR	<30 mL/min/1.73m ²
Creatinine , BUN ^a	Creatinine >0.5 mg/dL increase from baseline Creatinine >30% increase from baseline BUN >2× baseline BUN/Creatinine >30% increase from baseline
Glucose	>126 mg/dL (fasting) >200 mg/dL (non-fasting) <70 mg/dL (fasting or non-fasting)
HbA1c	>10%
hs-CRP	>10 mg/L
Albumin	<LLN
Hemoglobin	≥2 g/dL decrease from baseline and < LLN
LDL-C	≥25% increase from baseline
TG	≥1000 mg/dL
Other safety chemistry and hematology parameters ^b	<LLN or >ULN
Heart Rate	≤50 bpm and decrease from baseline ≥20 bpm ≥120 bpm and increase from baseline ≥20 bpm
SBP	≤95 mmHg and decrease from baseline ≥20mmHg ≥160 mmHg and increase from baseline ≥20 mmHg
DBP	≤45 mmHg and decrease from baseline ≥10 mmHg ≥110 mmHg and increase from baseline ≥10 mmHg
Weight	≥10% increase or decrease from baseline
LLN: Lower Limit of Normal; ULN: Upper Limit of Normal. Note: list all the values of the parameter from the patient if any criteria are met. ^a For these groups of parameters, include all parameters in the listing, by timepoint first. ^b Parameters not explicitly mentioned in this table, excluding lipids.
